Hypothesis	
The primary hypothesis regarding cooling performance is that at least 75% of the subjects will reach normothermia (core temperature $\leq 37.5^{\circ}\text{C}$) within 4 hours of starting COOLSTAT cooling.
 
The primary hypothesis regarding temperature maintenance is that at least 75% of the subjects' core temperatures remain between 36°C and 37.5°C for 80% of the steady state² time following the initial achievement of 37.5°C.

Outcomes	
Performance Outcomes
 
 1) This feasibility study is intended to confirm that the COOLSTAT system can cool within expected performance parameters and can reach and maintain normothermic cooling therapy over the study period. Subjects are expected to reach normothermia (core temperature $< 37.5^{\circ}\text{C}$) within 4 hours of starting COOLSTAT cooling. Subject temperatures are expected to be maintained within a 1.5°C temperature band, between $36^{\circ}\text{C} - 37.5^{\circ}\text{C}$, for 80% of the steady state time following the initial achievement of 37.5°C.¹

¹ This recognizes that some subjects will have short periods of break-through fever over the course of the study.

² If a subject must be disconnected from the CoolStat device for transport from the NCCU to another unit (e.g., to radiology or angiography suite), they will be reconnected to the device at steady state if their core temperature

	
2) Data collected will help to confirm cooling models and the control system algorithm by examining subject cooling response as a function of air flow rate and properties of the air supplied to the subjects.
 
3) The study will demonstrate that the COOLSTAT System can perform in the clinical setting and identify possible human and equipment interface refinements.
 
Safety Outcomes
 
Safety will be assessed by the following:
 
 4) The incidence and severity of all adverse events (including, but not limited to serious adverse events and non-related adverse events). 5) Assessment as to any potential contribution to the adverse event that may be device related or related to transnasal cooling therapy. 
Secondary Outcomes
 
This study may provide insight into the incidence of shivering, although the study design is not sufficiently powered to expect definitive conclusions.

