6.3 Primary Efficacy Endpoint and Success Criteria

This feasibility study should confirm that the COOLSTAT system has the ability to safely and adequately achieve and maintain normothermic cooling therapy with its control system over a specified period for subjects who were enrolled in the study.

This cooling aspect of the trial will be considered a success if at least 75% of the subjects achieve the following criteria:

- Cooling Performance: The subjects reach normothermia (core temperature $\leq 37.5^{\circ}\text{C}$) within 4 hours of starting COOLSTAT cooling.
- Temperature Maintenance: The subjects are held within a 1.5°C temperature band, between $36^{\circ}\text{C} - 37.5^{\circ}\text{C}$, for 80% of the steady state time following the initial achievement of 37.5°C .³

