6.10 Transition from 8-hour Cooling to 24-hour Cooling

The first 10 subjects will only be cooled for an 8-hour period, the results of which will be reviewed by the DSMB. For these first 10 subjects, if the subject still requires cooling at the end of 8 hours, the clinical site normothermia standard of care protocol will be used. If approved by the DSMB, the remaining subjects will transition to 24-hour cooling only upon satisfying all of the following criteria:

- No significant adverse events (SAEs) attributed to CoolStat
- CoolStat satisfied primary efficacy endpoint and success criteria on first 10 subjects (as specified herein):
 - 8 out of 10 subjects were cooled to $\leq 37.5^{\circ}\text{C}$ within 4 hours (based on final study endpoint of 75% subject achievement of this criteria)
 - 8 out of 10 subjects had core temp maintained between 37.5°C and 36°C for 80% of the steady state time following the initial achievement of 37.5°C .
- No findings of concern from ENT visual exam of upper airway post cooling
- Tympanic $> 34^{\circ}\text{C}$ and $< 39^{\circ}\text{C}$ during 8 hours of cooling, with no sustained period of more than 5 minutes $< 34^{\circ}\text{C}$ or more than 4 hours $> 39^{\circ}\text{C}$.
- No sustained increase of systolic blood pressure for > 5 minutes despite standard of care interventions that were above UMMC standard limits (specific to the indication being treated).
- DSMB reviews CRFs and agrees to increasing test period to 24 hours

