Similarly, per standard of care in the NCCU, a maximum allowed limit will be imposed for a sustained increase in ICP >5 minutes above max threshold despite standard of care intervention (using existing max institutional limits for the indication being treated). In this event, COOLSTAT use will be discontinued for that subject. Once the COOLSTAT is discontinued due to ICP elevation, it will not be restarted for that subject. However, the study team will continue to monitor ICP to see if it recovers back to baseline value after the COOLSTAT is turned off. The Investigator or their designee must complete an Adverse Event form detailing the event and the value of the ICP prior to, during and after the COOLSTAT was used. See Section 10.0 on procedures following the occurrence of an Adverse Event.

The Investigator or their designee will perform an initial cooling assessment 4 hours after COOLSTAT cooling has begun to determine if the subject has reached normothermia (≤ 37.5 C) sometime within the 4-hour cooling period. Starting from the initiation of normothermia, a subject's core temperature may fluctuate (within about 36.0-37.5 C), but

Transnasal Induction of Normotherapy in NCCU Fever Patients

if the core temperature $>39.0^{\circ}\text{C}$ for 4 hours, CoolStat treatment will be stopped and the subject will be switched to an alternative cooling method. If normothermia ($\leq 37.5^{\circ}\text{C}$) is not achieved within the 4-hour period, the Investigator or their designee will remove the subject from the COOLSTAT device. The subject will be classified as a treatment failure and placed on standard of care treatment at the discretion of the Investigator or their designee and manual data collection will continue per the instructions for Phase 2 in Section 9.4. NOTE – if the Investigator feels that the subject's temperature is approaching the target and the subject is being adequately cooled, CoolStat device operation can be allowed to continue beyond the 4-hour period. The Investigator should note if this is the case in the CRF.

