13.0 Statistical Analysis Plan

The primary efficacy analysis for cooling performance will be based on the evaluable populations of subjects who undergo cooling treatment with the COOLSTAT System. Analysis will be performed on treatment initiated and treatment completed populations. Subjects who achieve normothermia (core temperature $\leq 37.5^{\circ}\text{C}$) within 4 hours of starting COOLSTAT treatment and maintain normothermia for the duration of the treatment will be determined to have been treated successfully.

The primary efficacy analysis for temperature maintenance will be based on the evaluable population of subjects who maintain normothermia (core temperature between 36°C and 37.5°C) for at least 80% of the time following the initial achievement of 37°C will be determined to have been treated successfully.

The proportion of subjects fulfilling success criteria and 90% confidence intervals will be reported and compared to the a priori minimum acceptable criteria:

- at least 75% of the subjects will reach normothermia (core temperature $\leq 37.5^{\circ}\text{C}$) within 4 hours of starting COOLSTAT cooling, and
- at least 75% of the subjects' core temperatures remain between 36°C and 37.5°C for 80% of the steady state time following the initial achievement of 37.5°C .

Continuous measurements will be summarized using the mean and standard deviation. Categorical variables will be reported using percentages and confidence intervals. Data collected will be plotted to demonstrate the change in core temperature from baseline.

An exploratory analysis of participant subgroups will be performed, stratified by stroke presentation (ischemic versus hemorrhagic). Cooling performance and AEs will be evaluated by subgroup.

Double nostril air flow and single nostril air flow subjects will not be merged or directly compared. The results from subjects treated with single nostril flow will be analyzed separately from subjects treated with double nostril air flow.

Subjects 1 through 20 will be assigned to the double nostril air flow treatment group:

- Subjects 1 through 10 will be treated for 8 hours (N=10)
- Subjects 11 through 20 will be treated for 24 hours (N=10)

Subjects 21 through 30 will be assigned to the single nostril air flow treatment group

- Subjects 21 through 30 will be treated for 24 hours (N=10).
- Subjects 21 through 30 will be treated using a dose escalation model:
 - Dosing for this cohort (flow rate) will begin at 30 LPM.

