13.1 Primary Performance Outcome Analysis

The primary hypothesis regarding cooling performance is that at least 75% of the subjects will reach normothermia (core temperature $\leq 37.5^{\circ}\text{C}$) within 4 hours of starting COOLSTAT cooling.

The primary hypothesis regarding temperature maintenance is that at least 75% of the subjects' core temperatures remain between 36 °C and 37.5 °C for 80% of the steady state time following the initial achievement of 37.5 C.

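### The 75% success rule is stated inconsistently: one threshold over both criteria in some places, a threshold for each criterion in others, and the two can give opposite verdicts on the same subjects

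*Combined protocol and SAP*

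**What the plan says.** - **Section 6.3** (primary endpoint): "This cooling aspect of the trial will be considered a success if at least 75% of the subjects achieve the following criteria". Two bullets follow, one for reaching 37.5 °C within 4 hours and one for staying in the 36 to 37.5 °C band for 80% of steady-state time. The sentence says neither *both* nor *each*.
- **Section 1.0, Hypothesis, and 13.1**: two hypotheses, each with its own 75%. For cooling: "The primary hypothesis regarding cooling performance is that at least 75% of the subjects will reach normothermia". For maintenance: "The primary hypothesis regarding temperature maintenance is that at least 75% of the" subjects stay in the band for the required share of time. The Statistical Methodology row of 1.0 and the bullets in 13.0 repeat this form.
- **Section 6.10** (gate to 24-hour cooling): the primary endpoint is applied as two separate counts, "8 out of 10 subjects were cooled to" the target within 4 hours and "8 out of 10 subjects had core temp maintained between" the limits.
- **Section 13.0, first paragraph**: a joint definition. A subject must reach normothermia within 4 hours and "maintain normothermia for the duration of the treatment will be determined to have been treated successfully". The 80% allowance is absent.
- **Maintenance denominator**: the synopsis restricts it to subjects who were normothermic by 4 hours and continued. Section 6.10 counts out of all 10. The second paragraph of 13.0 describes its population by the success criterion itself, so no denominator can be read from it.
- **Section 9.3**: a subject who has not reached the target may stay on the device, since "CoolStat device operation can be allowed to continue beyond the 4-hour period" at the investigator's judgement. A subject can therefore miss the cooling criterion and still hold the band later.

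**The concern.** Section 6.2 gives the purpose as cooling to normothermia and keeping subjects there. A proportion of at least 75% on each of two criteria does not imply that 75% of subjects did both. If the rule is settled only after the data are seen, the more lenient sentence is available, and a device that cooled and held well under three quarters of the treated subjects could be reported as having met its primary criterion. Section 14.16 allows the data to be used in support of premarket notifications, so the wording of the success claim matters beyond this study.

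**Working it through.** **1. The plan's own sample size.** Section 6.6 uses one proportion, 0.90 assumed against 0.75 lowest acceptable, with z values 1.28 and 0.84:

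n = [(1.28·√(0.9·0.1) + 0.84·√(0.75·0.25)) / 0.15]² = 24.85, rounded up to 25.

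The stated 25 is reproduced. It rests on a single rate for subjects successfully cooled. There is no assumed rate for maintenance or for doing both.

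**2. Group size.** Section 13.0 keeps the air-flow groups apart, with 20 double-nostril and 10 single-nostril subjects. The check uses n = 20.

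**3. The rules in symbols.** Let R be the number cooled by 4 hours and M the number of those who also maintain (the synopsis population).

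- Separate rule: R/n ≥ 0.75 and M/R ≥ 0.75.
- Joint rule: M/n ≥ 0.75.

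Success is taken as the observed proportion reaching 75%, as the 8-of-10 counts in 6.10 do.

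**4. Smallest separate-rule pass, n = 20.** R must be at least 0.75 × 20 = 15. With R = 15, M must be at least 0.75 × 15 = 11.25, so 12. Cooling is 15/20 = 75% and maintenance 12/15 = 80%, and both pass. The joint proportion is 12/20 = 60%, which fails.

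**5. Direction.** If M ≥ 0.75n, then R ≥ M gives R ≥ 0.75n, and n ≥ R gives M ≥ 0.75R. Every joint pass is therefore also a separate pass. With these nested denominators, any disagreement is a separate-rule success that fails the joint rule.

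**6. How often the rules disagree, n = 20.** R ~ Bin(20, pc) and, given R, M ~ Bin(R, pm). The separate probability sums over R ≥ 15 and M ≥ 0.75R. The joint probability is P(Bin(20, pc·pm) ≥ 15).

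| Assumed pc / pm | pc·pm | Separate | Joint | Disagree |
|---|---|---|---|---|
| 0.90 / 0.90 | 0.81 | 0.962 | 0.836 | 0.127 |
| 0.85 / 0.85 | 0.7225 | 0.826 | 0.505 | 0.321 |
| 0.80 / 0.80 | 0.64 | 0.589 | 0.217 | 0.372 |

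**7. A common denominator.** If maintenance is counted over all 20 and late coolers kept on under 9.3 may contribute, 15/20 on each criterion is compatible with as few as 15 + 15 − 20 = 10 subjects (50%) doing both. This does not apply under the synopsis population, which excludes late coolers.

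**8. The 6.10 gate.** The gate asks for 8 maintained out of 10, not out of those cooled. If a maintainer must first have cooled by 4 hours, 8 maintained means 8 did both, and the joint rule passes too. Only if late coolers count can the overlap fall, to 8 + 8 − 10 = 6.

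**The case against.** The strongest reply is that the plan interprets itself. Section 6.3 is one loosely worded sentence with separately labelled bullets, 6.10 turns the same endpoint into two counts, and the synopsis, the 13.0 bullets and 13.1 agree with that. The study is also a feasibility study, called exploratory in 6.8. Much of this stands: the separate rule is the majority reading, and inserting a word or two in 6.3 may be all the sponsor needs there. It does not remove the conflict with the first paragraph of 13.0, and the plan does present prespecified success criteria.

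Three stronger readings are tempting, but the documents do not support them.

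- *Section 6.3 requires both criteria.* It may mean that, but it does not say so. The first paragraph of 13.0 cannot settle the matter, because it drops the 80% allowance and is therefore a different, stricter endpoint.
- *Nothing planned would show how many did both.* Under the synopsis population the maintenance numerator is exactly that count, and dividing by the number treated gives the joint proportion. The first paragraph of 13.0 also defines a joint success, and 13.0 plans to report the proportion fulfilling success criteria. What is missing is a clear plan to report the joint proportion on the 6.3 criteria over all treated subjects and to compare it with 75%.
- *The 10-subject gate could be passed with 8 cooled and 6 of those 8 maintaining.* It could not, because 6.10 asks for 8 of 10 maintained.

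**Conclusion.** The primary success rule needs reconciling before analysis. It appears in three forms: one threshold open to two readings (6.3), a stricter joint definition (first paragraph of 13.0), and a threshold per criterion (1.0, 6.10, the 13.0 bullets, 13.1). For the 20 double-nostril subjects the separate rule can be met with 60% doing both. Under the assumed rates the two rules disagree with probability 0.13 to 0.37, always with the separate rule the lenient one.

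These probabilities illustrate the size of the problem and are not taken from the plan. They assume success is judged on the observed proportion and that maintenance is analysed in subjects cooled by 4 hours. The documents give 0.90 for cooling only and no rate for maintenance. The documents do not establish which rule the sponsor intends, and the finding does not depend on it.

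**What to change.** - State one rule in 1.0, 6.3, 6.10, 13.0 and 13.1. If the per-criterion rule used in most places is intended, insert *each of* before *the following criteria* in 6.3. If the joint rule is intended, say *both* in every place and restate the assumed rate in 6.6 for the joint endpoint.
- Bring the first paragraph of 13.0 into line with the 80% of steady-state time used elsewhere.
- Use one maintenance denominator throughout, and say whether subjects who cool after 4 hours can count.
- Under either rule, report for each air-flow group the proportion of all treated subjects who meet both criteria, with its 90% CI, next to the two component proportions.

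**Cost.** The per-criterion route needs only wording and one extra proportion from data already collected. That proportion cannot exceed the cooling proportion and will usually look less favourable than either component. The joint route costs more, because 6.6 no longer fits. At an illustrative joint rate of 0.9 × 0.9 = 0.81 the plan's formula gives [(1.28·√(0.81·0.19) + 0.84·√(0.75·0.25)) / 0.06]² = 208.3, or 209 subjects, against the 25 stated. The sponsor would then have to justify a different assumed rate or present the joint result without a power claim.

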6.4 Safety Outcomes

An important outcome of this study is to assess the safety of high flow rate transnasal air delivery by the COOLSTAT device. The device safety will be addressed by the following:

³ This recognizes that some subjects will have short periods of break-through fever over the course of the study.

- The incidence and severity of all adverse events (including non-device-related adverse events) and the potential contribution to the adverse event that may be device related.
- Assessment by the investigator or their designee and attending physician(s) as to any adverse event that may be related directly to transnasal cooling.
- Confirmation based on a visual exam of the turbinates and upper airway that no clinically significant abnormal findings were attributable to transnasal air flow or the COOLSTAT device.

This study should also demonstrate that the COOLSTAT system can perform in the clinical setting.

The study may provide insight into the incidence of shivering, although the study design is not sufficiently powered to expect definitive conclusions.

6.5 Investigational Duration and Follow-up

This study will conclude when 30 subjects receive COOLSTAT Therapy.

6.6 Sample size calculations

The sample size was determined from the calculation below, using the following assumptions:

$$n = \left[\frac{z_{\alpha} \sqrt{p_0(1-p_0)} + z_{\beta} \sqrt{p_1(1-p_1)}}{p_1 - p_0} \right]^2$$

n: minimum sample size

$p_0 = 0.9$ Assumed proportion of subjects successfully cooled

$p_1 = 0.75$ Lowest acceptable proportion of subjects successfully cooled

$\delta = |p_1 - p_0| = 0.15$ Difference between ideal and minimum acceptable

Confidence (α): 90%

$$z_{95} = 1.28$$

Statistical Power (β): 80%

$$z_{80} = 0.84$$

n = 25 subjects completing treatment, therefore a sample size of 30 subjects was selected to allow for dropouts. The study will enroll up to 70 subjects, accounting for a 55% expected post-consent screen failure rate. Enrollment will stop once the 30th subject receives COOLSTAT therapy.

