 - The dose will be increased by 10 LPM if 3 consecutive subjects complete the study protocol with no serious adverse events (as listed in section 10.5) or unanticipated adverse device events.
 - Up to three doses will be evaluated in this cohort (30 LPM, 40 LPM, 50 LPM).
- The purpose of this cohort is to assess the safety of and optimal dose for the single nostril air flow configuration of the CoolStat.
- Each subject will be examined for adverse events, serious adverse events, and unanticipated adverse device events by an intensivist or otolaryngologist within 24 hours of completing CoolStat therapy.
- Each flow rate cohort must be evaluated by an intensivist or otolaryngologist prior to advancing the protocol to the next increased flow rate cohort.

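### Section 6.6 puts the assumed 90% in the null position and sizes one pooled group, so its 80% power does not hold against the 75% benchmark or in the unmerged groups of 20 and 10.

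*Combined protocol and SAP*

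**What the plan says.** Section 6.6 prints a one-sample formula in which z_alpha multiplies the standard deviation at p0 and z_beta the standard deviation at p1. It sets p0 = 0.9, described as "Assumed proportion of subjects successfully cooled", and p1 = 0.75, described as "Lowest acceptable proportion of subjects successfully cooled". Confidence is 90% with a z of 1.28 (subscripted 95), and power is 80% with a z of 0.84. The result is "n = 25 subjects completing treatment, therefore a sample size of 30 subjects was selected to allow for dropouts".

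Elsewhere the benchmark is 75%. Section 13.1 states: "The primary hypothesis regarding cooling performance is that at least 75% of the subjects will reach normothermia". Section 6.3 calls the cooling aspect a success if at least 75% of subjects meet the criteria, and section 6.10 applies this as 8 of 10. Section 13.0 adds: "The proportion of subjects fulfilling success criteria and 90% confidence intervals will be reported and compared to the a priori minimum acceptable criteria".

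Section 13.0 also divides the treated subjects. "Subjects 1 through 20 will be assigned to the double nostril air flow treatment group", and subjects 21 to 30 form the single-nostril group. It says that "Double nostril air flow and single nostril air flow subjects will not be merged or directly compared". Of the single-nostril group it says: "The purpose of this cohort is to assess the safety of and optimal dose for the single nostril air flow configuration of the CoolStat". No section gives a power or precision statement for 20 or for 10.

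**The concern.** Section 6.6 never uses the words null and alternative, but the formula fixes the roles. The proportion paired with z_alpha is the one tested, and the proportion paired with z_beta is the one at which power is computed. As printed, the 90% is the chance of not rejecting a true 90% rate, and the 80% is the chance of detecting a rate as low as 75%. The stated hypotheses ask whether the rate is at least 75%.

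The calculation also assumes a single group, which section 13.0 no longer has. And section 13.0 compares the 90% interval with 75% without giving the interval's sidedness, its method or what follows from the comparison.

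Section 6.6 is the plan's only justification of its size. A reader will take the 90% and 80% as properties of the 75% criterion in the groups that are reported. Section 14.16 foresees use of the data in premarket notifications and publications.

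**Working it through.** **Inputs.** From 6.6: p0 = 0.90, p1 = 0.75, z_alpha = 1.28, z_beta = 0.84, n = 25 raised to 30. From 13.0: groups of 20 and 10. From 6.3: success if the observed proportion is at least 75%, which is 15 of 20.

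**1. The plan's own figure.** n = [(z_alpha·√(p0(1−p0)) + z_beta·√(p1(1−p1))) / (p1−p0)]²

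= [(1.28 × 0.3000 + 0.84 × 0.4330) / 0.15]² = [(0.3840 + 0.3637) / 0.15]² = 24.85, so 25. It reproduces.

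**2. Roles exchanged** (null 0.75, alternative 0.90, same z values):

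[(1.28 × 0.4330 + 0.84 × 0.3000) / 0.15]² = [(0.5543 + 0.2520) / 0.15]² = 28.89, so 29.

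The exchange alone costs 4 completers and stays within the 30 treated.

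**3. The z label.** The standard normal quantile is 1.2816 at 0.90 and 1.6449 at 0.95. So 1.28 is the one-sided 90% value, and the subscript 95 is a slip. The lower limit of a two-sided 90% interval would use 1.645.

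**4. Exact binomial power, 75% as null, true rate 90%.**

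| n | Level | Successes needed | P(pass) at 75% | P(pass) at 90% |
|---|---|---|---|---|
| 30 (pooled, no dropout) | one-sided 0.10 | 26 | 9.8% | 82.5% |
| 25 | one-sided 0.10 | 22 | 9.6% | 76.4% |
| 20 | one-sided 0.10 | 18 | 9.1% | 67.7% |
| 20 | two-sided 90% interval excludes 75% | 19 | 2.4% | 39.2% |

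The last row is conditional: no section requires the interval to exclude 75%.

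**5. Exact power with 6.6 kept as written** (90% as null, lower tail at most 0.10, true rate 75%). At n=25, reject at 20 or fewer: 78.6%. At N=20, reject at 15 or fewer: 58.5%.

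**6. The stated rule.** P(X ≥ 15 | n = 20, p), for one criterion with all 20 evaluable:

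| True rate | Passes 15/20 | Fails |
|---|---|---|
| 90% | 98.9% | 1.1% |
| 75% | 61.7% | 38.3% |
| 70% | 41.6% | 58.4% |
| 60% | 12.6% | 87.4% |

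At 75% the device still meets the minimum, so a pass there is not an error. The 70% and 60% rows are the passes below the minimum.

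**7. Precision.** A result of 15/20 has a two-sided 90% interval of 0.544 to 0.896 (Clopper-Pearson) or 0.568 to 0.873 (Wilson).

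**8. Both criteria together.** Suppose, for illustration only, equal true rates on the two criteria, independence, and maintenance counted only among subjects normothermic by 4 hours (the evaluable population in the section 1.0 summary). Summing P(X = x) × P(at least 75% of x maintained) over x = 15 to 20 gives 96.2% at 90%, 33.6% at 75% and 15.1% at 70%.

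**The case against.** The strongest defence is that the orientation may be deliberate: treat 90% as expected performance and ask whether the data contradict it. In those terms the stated rule does what the 90% figure promises, since a true 90% device passes 15/20 with probability 98.9%. That stands, so it would be wrong to say that the 90% confidence fails in 6.6's own orientation. What fails is the 80%. The rule fails a true 75% device 38.3% of the time, and even the formal test of 90% at N=20 has 58.5% power.

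A reader might infer that a device truly at 70% has about a four in ten chance of trial success. The documents do not support that as a general statement. The 41.6% is for a single proportion with 20 evaluable subjects, whereas 13.0 joins two criteria. Success on both is less likely and depends on their correlation and on the maintenance denominator (15.1% under the assumptions in step 8). The 41.6% would apply to trial success only if 6.3 were read as one composite outcome per subject with a true composite rate of 70%.

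A reader might also infer that success requires the interval to lie above 75%, so that the trial has only 39.2% power. No section says so; the interval is to be reported and compared.

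It is also fair that the role exchange is small by itself (25 to 29), that the z label is trivial, that the study is described as feasibility and exploratory (6.7, 6.8), and that the single-nostril cohort has a safety and dose purpose. These points limit the weight of the finding. They do not make 6.6 describe the analysis in 13.0.

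**Conclusion.** The concern holds as a misstated justification of sample size. The arithmetic in 6.6 is correct for its inputs. The inputs are in the reverse of the roles that the 75% hypotheses call for, and the result describes a pooled group that 13.0 rules out. The stated 80% power is not delivered at N=20 in either orientation: 67.7% with 75% as null (one-sided 0.10), 58.5% with 90% as null. The split into unmerged groups matters more than the exchange of roles, since 30 pooled completers would still give 82.5%.

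Under the only stated success rule, a 90% device is rarely failed, but a 75% device is failed 38.3% of the time, not 80%.

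These figures rest on exact binomial calculation, one criterion at a time, and 20 evaluable subjects, which is the maximum for the double-nostril group. Dropouts, or a maintenance denominator limited to subjects who reached normothermia, would change them.

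The documents do not support going further and calling the trial invalid or its success rule unusable. For a feasibility study an observed-proportion criterion is acceptable, provided that its properties are stated correctly. This should be fixed before results are reported against 6.6.

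**What to change.** - **Section 6.6:** withdraw the statement that 25 completers give 90% confidence and 80% power. State that 30 treated subjects is a feasibility size, split 20 and 10. Replace the power claim with the exact pass probabilities of the stated rule for the double-nostril group, labelled as per criterion and with 20 as the maximum evaluable number (15/20: 98.9% at a true 90%, 61.7% at 75%, 41.6% at 70%, 12.6% at 60%). Add the precision at that size, for example 0.544 to 0.896 (Clopper-Pearson) for 15/20.
- **Null, alternative and z-values:** leave them out of 6.6 unless a test is intended. If one is, use null 0.75 and alternative 0.90, state the sidedness, and give the exact power at N=20.
- **Sections 6.3 and 13.0:** keep an observed proportion of at least 75% as the feasibility criterion. In 13.0, say that the 90% interval is descriptive, and name its method and sidedness.
- **Section 13.0:** say whether the 75% criterion applies to the single-nostril cohort, given its safety and dose purpose.

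Cost: a text amendment, which under 14.15 needs FDA approval before implementation, and a less favourable printed case for the trial size. No subjects are added, and the success rule, treatment and conduct do not change.
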